5.1.8 Abdominal MRI

Abdominal MRIs should be considered at the timepoints specified in Appendix A to provide a more accurate quantification of liver and spleen volume.

Abdominal MRIs are considered optional in this study. Investigators are encouraged to obtain abdominal MRIs in subjects receiving general anesthesia and/or sedation for other procedures at a scheduled imaging timepoint. To allow flexibility in scheduling MRIs, a broad time window is given for each MRI assessment in Appendix A. For example, the baseline MRI may be obtained at any time from Screening through the Week 0 study visit.

Because MRI can provide important information on liver and spleen volume that can be related to expected normal values abdominal MRIs should be obtained during the treatment phase, where feasible, even if a subject did not provide a baseline MRI.

All imaging scans will be acquired and the results interpreted by a magnetic resonance technician or other qualified individual using standardized imaging protocols.

Refer to the Imaging Manual for instructions on image acquisition and analysis.

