- Abdominal MRI should be considered in subjects receiving general anesthesia and/or sedation for other procedures at the indicated timepoints. The Screening MRI may be obtained up to 8 weeks of treatment. There should be at least 3 months between each MRI. (Either a MRI or Ultrasound should be performed at a given timepoint.)
- 6 CBC/hematology, chemistry liver function tests, lipid panel, ferritin, urinalysis and coagulation studies (see Section 5.1.11). Prior to any dose change, serum lipid, serum liver, hematology, chemistry, ferritin, and hs-CRP shall be obtained. Serum lipid and serum liver assessments should be taken 4, 8, and 12 weeks following any study drug or lipid lowering medication change.
- 7 If blood volume is limited, refer to Section 5.1.11 for tiered assessments.
- 8 DNA sample should be collected at Screening or at the earliest possible visit thereafter based on blood volume threshold, unless a stored DNA sample is already available for the subject.
- 9 Refer to Section 5.1.14 for PK sampling timepoints
- 10 If the screening labs were performed within 2 days of Week 0 then the Week 0 labs do not need to be performed.

Page 63 of 66

ALEXION PHARMACEUTICALS, INC. PROPRIETARY AND CONFIDENTIAL:
DO NOT COPY OR DISTRIBUTE WITHOUT PERMISSION

LAL-CL08 Protocol Amendment 3.0 08 December 2015

Schedule of Assessments: Week 17 through Study Completion*

											epeating	Annually	Follow-up/			
	W 17	W 18	W 19	W 20	W 21	W 22	W 23			Every Week	Every Month	Every 2 Months (8 weeks)	Every 3 Months (12 weeks)	Every 6 Months (24 weeks)	(Week 48, Week 96, Week 144)	Early Withdrawal
	± 2 days	± 2 days	± 2 days	± 2 days	± 2 days	± 2 days	± 2 days	± 2 days	study	± 2 days	± 2 days	± 2 days	± 5 days	±15 days	±15 days	30 (+7) days
Physical Exam ¹	days	days	days	X	days	days	days	X	of s	dayo	dayo	dayo	X	days	dayo	X
Anthropometrics				Х				Х	end o		X ⁶		X ⁶			Х
Vital Signs ²	Х	Х	Х	Х	Х	Х	Х	Х	l e	Х						
12-lead ECG			ŀ	f clinicall	y indica	ted			until		If clinically indicated					
Denver II								Х	าร					Х		Х
Abdominal Ultrasound								Х	essments						Х	
Abdominal MRI								X ⁷	ess						X ⁷	
Liver Biopsy									Asse						Х	
Clinical Laboratory Assessments ^{3, 4}				Χ ^P				Χ ^P				X ^{8,P}	X ^{8,P}			Х
Exploratory Biomarkers ³								Х	Repeating					Х		Х
PK Sample ^{3, 5}						Х			1 -						X_{g}	
Sebelipase Alfa Infusion ¹⁰	Х	Х	Х	Х	Х	Х	Х	Х		Х						
Anti-drug Antibody				Х				Х					Х			Х
Adverse Events									(CONTINU	JOUS					

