#### 5.2.2. Tertiary Endpoint(s)

Additional exploratory efficacy parameters include changes and percent changes from baseline in:

- Alkaline phosphatase, gamma glutamyltransferase (GGT), albumin, and bilirubin (direct, indirect, and total)
- Liver and spleen size/volume, as measured by ultrasound or magnetic resonance imaging (MRI)
- Platelet levels
- Serum lipid levels (total cholesterol, triglycerides, high density lipoprotein [HDL], and low density lipoprotein [LDL])

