# 7.3. Efficacy Analyses

Efficacy will be examined on the FAS. For the continuous endpoints, the observed values, change from baseline and percent change from baseline at each time of assessment will be summarized, and may include 95% confidence intervals (e.g. for time points with  $\geq 2$  observed data points).

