#### 7.3.1.2. Abdominal Magnetic Resonance or Abdominal Ultrasound

Change and percent change in liver and spleen volume in multiples of normal and fat content will be calculated from Baseline and tabulated for each evaluation time point. Multiples of normal are defined in Section 9.4.10. Change from baseline will only be calculated if the same mode of assessment, MRI or ultrasound, was used at baseline and post-baseline. Data will be summarized for the endpoints as continuous variables.

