#### 7.3.1.5. Exploratory Efficacy Analyses

Exploratory analyses of the effect of ADAs on the efficacy of SBC-102 may be explored using stratified analyses on efficacy endpoints.

Observed values and changes and percent changes from baseline in other exploratory efficacy endpoints may be tabulated for each evaluation time point. These will include changes in

liver and spleen size/volume, as measured by ultrasound or magnetic resonance imaging (MRI). Liver and spleen volumes will be presented in statistical outputs as multiples of normal (where normal is defined as 2.5% of body weight for liver and 0.2% of body weight for spleen); changes will be calculated if the same method was used at baseline and the post-baseline time point;

Shift tables may be used to tabulate dietary changes, including shift from low-cholesterol diet to unrestricted diet if sufficient data exist for summary.

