#### 9.4.8 Definition of Baseline Values and Change from Baseline

#### 9.4.8.1 Baseline

Baseline is defined as the last available assessment prior to the start of the first infusion of sebelipase alpha. If any Baseline laboratory analyte is evaluated at both the local and the central laboratory, then the central laboratory results will be used for analysis.

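### The MRI footnote to the Screening–Week 16 schedule conflicts with the ultrasound schedule, the baseline MRI window and the SAP's same-mode rule, so some children can lack change values for liver and spleen size

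*Protocol*

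**What the plan says.** **Schedule, Screening to Week 16 (Protocol Appendix A).** Ultrasound is marked at Week 0 and Week 12. MRI is marked at Screening and once more late in the same table. The MRI footnote says "Either a MRI or Ultrasound should be performed at a given timepoint" and also "The Screening MRI may be obtained up to 8 weeks of treatment".

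**Schedule, Week 17 onward.** Ultrasound and MRI are both marked at Week 24 and annually. The MRI footnote to this table sets a time window and contains no either/or sentence.

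**Protocol body.** Section 5.1.7 states that ultrasound will be done at the Appendix A timepoints and mentions no substitution. Section 5.1.8 makes MRI optional and ties it to anaesthesia or sedation for other procedures. It encourages on-treatment MRI even without a baseline MRI, and it gives the baseline window: "the baseline MRI may be obtained at any time from Screening through the Week 0 study visit".

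**SAP.** Section 9.4.8.1: "Baseline is defined as the last available assessment prior to the start of the first infusion of sebelipase alpha". Section 7.3.1.2: "Change from baseline will only be calculated if the same mode of assessment, MRI or ultrasound, was used at baseline and post-baseline". Section 7.3.1.5 repeats the restriction: "changes will be calculated if the same method was used at baseline and the post-baseline time point". Section 7.3.1 says that missing data are in general not imputed. For continuous efficacy endpoints, section 7.3 says "the observed values, change from baseline and percent change from baseline at each time of assessment will be summarized".

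**The concern.** The same-mode rule in the SAP is sound, because a difference between an MRI value and an ultrasound value mixes method with response. It works only if data collection produces same-mode pairs. The footnote lets a site collect images that cannot be paired, and its 8-week allowance lets an image called Screening be taken after treatment has begun.

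Hepatomegaly and splenomegaly form part of a secondary objective, and imaged organ size is its only quantitative imaging measure. The endpoint itself is tertiary (SAP 5.2.2). With at most 10 children, each lost pair is visible. If a post-dose image were instead accepted as baseline, as the exploratory allowance in Protocol 8.1 would permit, up to 8 weeks of response would sit inside the baseline.

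**Working it through.** The plan has no figure to reproduce: there is no sample-size calculation and no expected rate of mode switching. The check is a comparison of texts, followed by an illustration.

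**Step 1. What a site following the footnote can produce**

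- *No pre-dose image.* A site treats the Screening MRI and the Week 0 ultrasound as one imaging timepoint, omits the ultrasound, and does the MRI at, say, Week 6. The footnote permits this; 5.1.7 and 5.1.8 do not. Under SAP 9.4.8.1 the child has no baseline image, so there is no change value at any timepoint. The missing pre-dose image cannot be recovered later.
- *Ultrasound baseline, MRI instead of the Week 12 ultrasound.* The modes differ, so SAP 7.3.1.2 gives no change value at Week 12. The child has a value again at the next ultrasound.
- *MRI-only baseline, taken before the first infusion.* Later ultrasounds give no change value. Only further MRIs can, and those are optional.
- *Ultrasound baseline, Week 24 and annual visits.* Both rows are marked and no sentence waives either. On a literal reading the ultrasound is still done and the child has a change value.
- *Both modes before the first infusion.* Nothing is lost, whichever mode follows.

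**Step 2. Size of the loss at one timepoint (illustration)**

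Inputs: up to 10 subjects (Protocol 4.2); 95% t-intervals for continuous endpoints (Protocol 8.1, SAP 7); no general imputation (SAP 7.3.1). The number without a same-mode pair, k, is an assumption, shown from 0 to 5. Deaths, withdrawals and missed scans are set to zero, and the SD is held constant.

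n = 10 − k; half-width in SD units = t(0.975, n − 1) / √n.

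| k | n | t(0.975, n − 1) | half-width (SD) | wider than k = 0 |
|---|---|---|---|---|
| 0 | 10 | 2.2622 | 0.715 | – |
| 1 | 9 | 2.3060 | 0.769 | 7% |
| 2 | 8 | 2.3646 | 0.836 | 17% |
| 3 | 7 | 2.4469 | 0.925 | 29% |
| 4 | 6 | 2.5706 | 1.049 | 47% |
| 5 | 5 | 2.7764 | 1.242 | 74% |

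If each child independently had a 10% chance of a mismatch, the chance of losing at least one of 10 would be 1 − 0.9^10 = 65%. At 30% it would be 1 − 0.7^10 = 97%. Both rates are assumptions.

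**The case against.** A reader might infer that MRI may replace ultrasound at every imaging timepoint, so that a child with ultrasound at Week 0 and MRI near Week 24 has no Week 24 change value. The documents do not support this. The either/or sentence stands only in the footnote to the Screening–Week 16 table, and 5.1.7 keeps ultrasound in force at Week 24 and annually. The sentence can even be read as asking for at least one scan rather than waiving one. That ambiguity is itself a reason to reconcile the wording.

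A reader might also infer that affected children leave the liver and spleen result altogether. They do not. The same-mode rule limits change and percent change. Observed values are still summarised and all data are listed. Volumes are expressed as multiples of normal, which can be read without a baseline. What remains open is whether MRI and ultrasound values are pooled in those summaries; the SAP does not say.

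Three further points carry weight:

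- The endpoint is tertiary. Liver and spleen are also examined clinically at each physical examination, and abdominal circumference is summarised, so the objective does not rest on imaging alone.
- MRI is optional and tied to sedation, so one or two mismatches are as plausible as four or five. Intervals are optional and descriptive.
- A child with a post-dose Screening MRI may still have had the Week 0 ultrasound, in which case ultrasound change is intact.

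None of this removes the conflict between the footnote, 5.1.7, 5.1.8 and the SAP.

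**Conclusion.** The concern holds in limited form. The footnote contradicts 5.1.7 on whether ultrasound is always done, and 5.1.8 on when the baseline MRI window closes. Combined with the SAP's baseline definition and same-mode rule, it can leave a child with no valid baseline image, or without a change value at Week 12. A child with an MRI-only baseline gets no change value from later ultrasounds.

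The cost falls on precision and completeness for a tertiary endpoint: a half-width of 0.77 to 1.24 SD instead of 0.72 SD at the affected timepoint, for an assumed 1 to 5 of 10 children without a pair. It is tempting to add that the loss is selective because MRI goes to children sedated for other procedures. That is plausible, but the documents give neither a switch rate nor anything that fixes the direction of a bias. The primary safety objective is untouched. Because a missing pre-dose image cannot be replaced, the wording should be corrected.

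**What to change.** 1. **Protocol Appendix A, MRI footnote.** Replace the either/or sentence with: *Ultrasound is performed at every scheduled imaging timepoint, including before the first infusion; optional MRI may be added but does not replace it.* This agrees with 5.1.7 and leaves MRI optional as in 5.1.8. A rule to repeat whichever mode was used at baseline would be worse, because it would make MRI compulsory for a child whose baseline was MRI.
2. **Same footnote, MRI window.** Align it with 5.1.8 and SAP 9.4.8.1. An MRI after the first infusion is labelled on-treatment and is not used as baseline in the change tables.
3. **SAP 7.3.1.2.** Tabulate MRI and ultrasound separately, and report at each timepoint how many children lack a same-mode pair. This step helps even if images have already been collected.

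The cost is a few sentences in each document. The one practical downside is that the ultrasound, already scheduled and non-invasive, is no longer waived when an MRI is done.

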5.1.9 Vital Signs

Vital signs will include pulse rate, respiratory rate, systolic and diastolic blood pressure and core body temperature (rectal or oral). Assessment of pulse rate and blood pressure will be taken after the subject has been in a supine position.

Vital signs will be measured at the timepoints specified in Appendix A. On dosing days, vital signs will initially be recorded pre-infusion, every 15 (±5) minutes during infusion and every 30 (±10) minutes from 0 to 4 hours after completion of the infusion. After a subject has successfully completed at least 1 year of treatment with no occurrence of moderate-to-severe IARs, the post-infusion period for vital sign monitoring may be shortened from 4 hours to 2 hours.

Additional readings may be taken at the discretion of the Investigator and in the event of an IAR.

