7.1.3 Adverse Events of Special Interest (Infusion-Associated Reactions)

Infusion-associated reactions (IARs) will be considered AEs of special interest. Any AE that occurs during the infusion or within 4 hours after the infusion is completed and is assessed by the Investigator as at least possibly related to study drug will be designated as an IAR. In addition, if, at any time during the study, the Investigator observes symptoms that he/she considers to be consistent with an IAR or hypersensitivity reaction related to administration of study drug, the symptoms should be recorded as an AE(s) and designated as an IAR(s). Individual adverse event terms should be recorded rather than the terms, IAR or Infusion Associated Reaction.

As with any ERT, medications and equipment for the treatment of hypersensitivity reactions must be available for immediate use in case of unexpected, severe hypersensitivity reaction. These supplies include, but are not limited to, oxygen, acetaminophen, antihistamines (e.g., diphenhydramine, parenteral and oral), corticosteroids, epinephrine, and cardiopulmonary resuscitation devices.

General guidelines for classifying the severity of a reaction are provided in Appendix B.

For similar biological products, most acute IARs occur within 2 hours of the infusion. Signs of a possible acute IAR may include:

 Hyperemia, flushing, fever and/or chills, nausea, pruritus, urticaria, gastro-intestinal symptoms (vomiting, diarrhea, abdominal cramping), cardiopulmonary reactions, including chest pain, dyspnea, wheezing, stridor, hypotension or hypertension

If any of the above signs and symptoms are observed during the infusion and the subject remains hemodynamically stable:

- The infusion rate must be slowed (reduced to half the rate being given at the onset of the event, e.g., from 10 mL/hr to 5 mL/hr) and the infusion time extended in accordance with the institutional standard of care. The infusion rate may be decreased further by 25% if symptoms persist. Once the event has resolved, the infusion should continue for a minimum of 30 minutes at the reduced rate before the rate is increased to 75% of the original rate on the infusion schedule. If the subject tolerates the infusion at 75% of the original rate for at least 30 minutes the original rate may be restored for the remainder of the infusion.

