Concomitant Medications/ Therapies		CONTINUOUS														

^{*} All visits will be calculated from Week 0; consecutive infusions must be administered at least 5 days apart.

P Pre-dose

- 1 All physical examinations will include liver, spleen, and lymph node assessments. In addition, digital photographs (full length and abdominal close up) will be obtained at Weeks 20 and 24 and annually thereafter.
- 2 During infusion visits, vital signs will initially be measured pre-dose, every 15 (±5) minutes during the infusion, and every 30 (±10) minutes from 0 to 4 hours post-infusion (see Section 5.1.9). After a year of treatment with no IARs, the post-infusion monitoring period may be shortened from 4 hours to 2 hours.
- 3 If blood volume is limited, refer to Section 5.1.11 for tiered assessments.
- 4 CBC/hematology, chemistry, liver function tests, lipid panel, ferritin, urinalysis and coagulation studies, (see Section 5.1.11). Prior to any dose change, serum lipid, serum liver, hematology, chemistry, ferritin and hs-CRP shall be obtained. Serum lipid and serum liver assessments should be taken 4, 8, and 12 weeks following any study drug or lipid lowering medication dose change.
- 5 Refer to Section 5.1.14 for PK sampling timepoints.
- 6 Weight will be measured at all visits; Recumbent length or height, and abdominal circumference will be measured at every 3 month visits; head and mid-upper arm circumference will also be measured at all every 3 month visits through Week 96
- 7 Abdominal MRI should be considered in subjects receiving general anesthesia and/or sedation for other procedures. The MRI may be conducted at any time from Week 24 through Week 32, and then annually, and should be scheduled at least 3 months after the preceding MRI assessment.
- 8 Repeating assessments will be performed every 2 months through Week 48 and every 3 months thereafter until study completion.
- 9 PK samples will be collected only at the first annual assessment (Week 48).
- 10 Subjects who are on treatment for at least 96 weeks and have been on a stable dose for at least 24 weeks, may transition to an every other week dosing schedule at the same dose they received on the weekly dosing schedule at the discretion of the PI with Sponsor consultation.

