#### 7.2.2.2. AEs, SAEs and IARs by System Organ Class (SOC) and Preferred Term (PT)

The frequencies of TEAEs, SAEs, IARs and percentage of patients with events will be tabulated by PT within SOC. Patients are counted once in each SOC and PT. Percentages will be based on the total number of patients in the specific analysis population. SOCs will be listed in order of frequency of occurrence.

Frequencies will also be presented by the classifications of severity and causality. In addition, frequency of AEs, SAEs, and IARs will be presented for time periods spanning the entire course of treatment with SBC-102: from the start of dosing with SBC-102 in this study to 3 months after the first dose; >3 to 6 months; >6 to 12 months; >12 to

Alexion Pharmaceuticals LAL-CL08

18 months; >18 to 24 months; and >24 months. The incidence of AEs leading to study discontinuation will also be summarized.

Summaries of adverse events will be summarized by anti-drug antibody (ADA) status. Subjects who developed ADA vs subjects who did not develop ADA. For subjects who developed ADA, only those AEs reported on or after the first time ADA were identified will be summarized. The number of subjects experiencing any TEAE will be presented overall and by relationship to study drug, with AE specific details presented by SOC and PT, also by relationship to study drug. This table will also be generated for all TESAEs and for all IARs.

Detailed listings of patients who experience AEs, SAEs and IARs will be presented. Detailed listings will include severity and relationship to treatment, seriousness, as well as action taken regarding study treatment, other action taken, and patient outcome. A separate listing of patients who discontinued from the study due to a treatment-emergent AE will also be provided.

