#### 7.2.5. Vital Signs

Within each visit (infusion), descriptive summaries of both maximum and minimum result and both maximum minimum increase from the pre-infusion assessment will be summarized.

Observed values and change from pre-infusion will be presented for the following vital sign parameters:

- Body temperature
- Pulse rate
- Blood pressure
- Respiratory rate

A listing of the vital signs measurements will be also provided.

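### The condition for cutting post-infusion vital-sign monitoring from 4 to 2 hours is stated two ways, and infusion-reaction tables after month 12 may mix the two monitoring lengths

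*Protocol*

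**What the plan says.** Appendix A, footnote 2 to the schedule from Week 17 to study completion, is attached to the vital-signs row and refers the reader to Section 5.1.9. It then states its own condition: "After a year of treatment with no IARs, the post-infusion monitoring period may be shortened from 4 hours to 2 hours".

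Protocol 5.1.9 states a different one, allowing the reduction from 4 hours to 2 after "at least 1 year of treatment with no occurrence of moderate-to-severe IARs". SAP 5.1.1.2 carries the 5.1.9 condition, not the footnote's.

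Protocol 7.1.3 defines an IAR in two ways. The timed part covers "Any AE that occurs during the infusion or within 4 hours after the infusion is completed", if the Investigator judges the event at least possibly related. The untimed part applies "if, at any time during the study, the Investigator observes symptoms that he/she considers to be consistent with an IAR" or a hypersensitivity reaction to the drug. The same section adds: "For similar biological products, most acute IARs occur within 2 hours of the infusion".

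On reporting, SAP 7.2.2.2 says that "frequency of AEs, SAEs, and IARs will be presented for time periods spanning the entire course of treatment with SBC-102". The periods, also given in Protocol 8.8.1, are the first 3 months, >3 to 6, >6 to 12, >12 to 18, >18 to 24 and >24 months from first dose. SAP 7.2.5 plans, within each infusion visit, "descriptive summaries of both maximum and minimum result". Neither SAP section mentions the length of monitoring.

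**The concern.** There are two linked problems.

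The first is a plain conflict in current text. A site can follow one passage and depart from the other, and whether a child with mild reactions only is monitored for 2 or 4 hours depends on the page consulted.

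The second concerns the reading of the safety tables. One year of treatment is both the earliest point at which monitoring may be shortened and the line between two reporting periods. IAR incidence is among the safety endpoints in SAP 5.1.1, and Protocol 8.8.1 foresees extra displays of IAR frequency and severity over time. A reader who sees fewer IARs after month 12 will be inclined to credit growing tolerance. Part of the fall could instead come from shorter on-site observation, and that shorter observation applies only to children whose first year was already free of reactions, or of the more severe ones. The SAP plans no display that holds the observation window constant.

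**Working it through.** **1. The two conditions side by side**

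| First-year history | Protocol 5.1.9 and SAP 5.1.1.2 | Appendix A footnote 2 |
|---|---|---|
| No IAR | may shorten | may shorten |
| Mild IARs only | may shorten | may not shorten |
| Any moderate or severe IAR | may not shorten | may not shorten |

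The texts disagree in the middle row only.

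**2. What changes when monitoring is shortened**

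Inputs: readings every 30 minutes after infusion (Protocol 5.1.9); 4 hours or 2 hours.

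- Monitored time: 240 to 120 minutes, a 50% reduction.
- Scheduled post-infusion readings, counting time 0: 240/30 + 1 = 9, against 120/30 + 1 = 5.

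**3. How much of the study it can reach**

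Inputs: treatment of at least 18 months expected, up to 3 years (Protocol 3.2.3); optional every-other-week dosing from Week 96.

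- Share of treatment time after month 12: (36 − 12)/36 = 67% at 3 years; (18 − 12)/18 = 33% at 18 months.
- Reporting periods that can be affected: three of six.
- Infusions per child over 3 years, at most: Weeks 52 to 155 weekly = 104. With every-other-week dosing from Week 96: 44 + 30 = 74.
- If a year is read as the Week 48 annual visit, the change could begin at 48 × 7/365.25 × 12 = 11.0 months, inside the >6 to 12 month period.

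These are ceilings, because shortening is permitted and not prescribed.

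**4. Possible loss of IARs**

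The documents give no distribution of onset times, so this is a sensitivity range. Let q be the share of all IARs that start 2 to 4 hours after infusion, and s the share of those still recorded without on-site monitoring. Both are assumptions. At infusions with shortened monitoring, capture relative to 4-hour monitoring is 1 − q(1 − s).

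| q | s = 0 | s = 0.5 | s = 0.8 | s = 1 |
|---|---|---|---|---|
| 5% | 95% | 97.5% | 99% | 100% |
| 10% | 90% | 95% | 98% | 100% |
| 25% | 75% | 87.5% | 95% | 100% |
| 50% | 50% | 75% | 90% | 100% |

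The protocol's statement that most acute reactions fall within 2 hours puts q below 50%, so the last row is a limit. If only a fraction f of a period's infusions is shortened, and IARs are spread evenly over infusions, capture is 1 − f·q(1 − s). For example, f = 0.5, q = 10%, s = 0.5 gives 1 − 0.025 = 97.5%.

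The SAP tables give the percentage of subjects with an event, counting each subject once per term. With the maximum of 10 subjects, one child whose only reaction in a period goes unrecorded moves that percentage by 1/10 = 10 points.

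**5. Vital-sign extremes**

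A maximum over fewer readings tends to be lower. Treating readings as independent normal values and assuming 8 readings during infusion, the expected maximum is 1.79 SD for 8 + 9 = 17 readings and 1.67 SD for 8 + 5 = 13, a gap of 0.126 SD. With a common correlation ρ between readings the gap scales by √(1 − ρ): about 0.09 SD at ρ = 0.5 and 0.06 SD at ρ = 0.8. The direction is clear, but the size is modest and rests on assumed inputs.

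**The case against.** A reader might infer that, after the switch, children are observed for less time than the IAR definition requires. The documents do not support that. The 4-hour window in Protocol 7.1.3 classifies events; it sets no period of observation. What may be shortened is vital-sign monitoring. Adverse-event collection remains continuous, Protocol 7.3 requires specific questioning at each contact, and events within 24 hours of an infusion are recorded with clock time. A reaction at 3 hours that a parent reports, judged at least possibly related, is still an IAR.

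Nor do the documents say that every later period is observed less. Shortening is optional and conditional, may come later than month 12, and leaves children who do not qualify on 4 hours. Those who qualify had few or no reactions, so they may contribute few IARs anyway.

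The by-period tables are descriptive, with no testing and up to 10 subjects. For vital signs, the SAP plans no comparison across month 12, and Protocol 8.8.3 also summarises change at each time point, which does not depend on the number of readings.

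These points stand and limit the claim, but they do not remove it. The 24-hour telephone call for outpatients covers only the first two infusions at 1 and at 3 mg/kg (Protocol 3.1). Later, the next planned contact may be the next infusion, one or two weeks on. Hypotension and hypertension are listed as IAR signs, and in a small child at home either could pass unnoticed without a reading.

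**Conclusion.** The conflict between Appendix A footnote 2 and Protocol 5.1.9 with SAP 5.1.1.2 is certain and affects children with mild IARs only in the first year. The passages must be reconciled; this review does not say which condition is right.

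The statistical consequence is narrower. IAR periods after month 12 may mix 2-hour and 4-hour on-site monitoring, so part of any apparent fall could reflect reduced on-site detection. Its size cannot be derived from the documents and may be small. The range in the working depends on assumed onset times and assumed reporting by families. The vital-sign calculation depends on an assumed number of readings and, for its largest value, on independence; it does not justify discarding data. No sample size, power or test is affected, because the study has none.

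**What to change.** - **Protocol 5.1.9, SAP 5.1.1.2 and Appendix A footnote 2:** reconcile to a single condition, worded identically in all three places.
- **SAP 7.2.2.2:** keep the IAR-by-period table under the full definition. Add a supplementary table with the same periods, limited to IARs with onset during the infusion or within 2 hours after it ends. That window is covered on site in every period, whichever monitoring length applies.
- **SAP 7.2.5:** keep the maxima and minima over all readings. If a version limited to 2 hours after infusion is wanted, make it supplementary. Replacing the present summary would drop the 2-to-4-hour readings of the first year, when monitoring is at its fullest.

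The cost is a wording change plus one or two extra displays. Protocol 7.3 already calls for clock times for events within 24 hours of infusion, and applying the 4-hour definition already needs the time at which the infusion ended. No new data collection is needed for these tables.
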